4.1.3 Classification and Stratification Factors

4.1.3.1 Classification Factors:

- Primary Study (RCT) Participation: Yes vs. No.

4.1.3.2 Stratification Factors:

- Gender: Male vs. Female
- Race: White vs. Others
- Age: ≤ 65 vs. > 65 years
- Education level: No college vs. College vs. Professional/Graduate

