With the completion rate for both T0 and T1 surveys at approximately 60% (as analyzed in May 2018) and the goal of evaluable sample size at 200/arm (at least for the analysis of changes between T0 and T1), the accrual goal of the primary intervention study needs to be inflated from 400 to 670 patients in order to maintain sufficient power for detecting proposed changes from T0 to T1 and changes in knowledge and cancer specific from T0 to T2 (as described in the preceding paragraph). With the completion rate for both T0 and T2 surveys at approximately 45% (as analyzed in May 2018), the projected evaluable sample size of 150 patients/arm can give the power of 72% for changes in knowledge and 95% for changes in cancer specific distress from T0 to T2. These 670 patients will be randomized 1:1 between the two arms, and the randomization will be stratified by gender, race, age (> 65 vs. ≤ 65), and education level. As of this analysis time, 320 patients have been enrolled into the primary intervention study. The current COMET accrual rate is approximately 15 patients per month (based on the last 3 months). Assuming 15, 20 or 25 patients per month (as more expansion sites are added over time) can be accrued to COMET from the select sites, it is expected to take 23, 17 or 14 additional months, respectively, to complete Step 1 accrual of 670 patients.

The original accrual plan posed a limitation on White patients at 80% of the accrual goal to ensure diversity of patients. Given that the accrual of this study might terminate early if the funding of this study ends, the accrual limitation on White patients is being lifted to ensure the maximal number of patients enrolled before funding ends.

Power for various sample sizes

Variable	Change score time period	Sample Size Per Arm	Power for p< 0.005, 2-sided	Change Score Group 1	Change Score Group 2	Standard Deviation Group 1	Standard Deviation Group 2
State Anxiety	T0 to T1	100	98%	2.71	-2.78	8.24	7.43
State Anxiety	T0 to T1	150	100%	2.71	-2.78	8.24	7.43
State Anxiety	T0 to T1	200	100%	2.71	-2.78	8.24	7.43
State Anxiety	T0 to T1	300	100%	2.71	-2.78	8.24	7.43
State Anxiety	T0 to T1	400	100%	2.71	-2.78	8.24	7.43
State Anxiety	T0 to T1	61	85%	2.71	-2.78	8.24	7.43
IES-Total	T0 to T1	100	100%	0.29	-1.78	1.70	3.19
IES-Total	T0 to T1	150	100%	0.29	-1.78	1.70	3.19
IES-Total	T0 to T1	200	100%	0.29	-1.78	1.70	3.19
IES-Total	T0 to T1	300	100%	0.29	-1.78	1.70	3.19
IES-Total	T0 to T1	400	100%	0.29	-1.78	1.70	3.19

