7.1.2 Analysis Plan

Outcome change scores (primary endpoints) between time points for each study participant will be calculated. Two-sample T-tests will be conducted first to evaluate whether there is any difference in outcome change scores (with respect to the primary endpoints) between MATCH patients and non-MATCH patients. If differences are observed, the analysis described below will be performed separately for each cohort.

Two-sample T-tests assuming unequal variances will be used for the primary analyses of the change scores between arms. An intention-to-treat approach will be used in which the effect between randomized arms is evaluated, regardless of any treatment crossover. In secondary analyses of the primary endpoints, demographic characteristics between the two arms will be evaluated using T-tests and Fisher's Exact Tests to investigate if the arms were unbalanced with respect to potential confounders. If any potential confounders (in particular age, race/ethnicity and health literacy) are found to have means/proportions that are different between the arms at a p-value of less than 0.1, we will examine the treatment effect in multiple linear regressions of the outcomes in which the randomized arms will be included as a binary (0/1) dummy indicator and all potential confounders that have a p-value < 0.1 will be included as covariates. These analyses will be repeated using the as-treated approach in which we compare differences between the interventions the patient actually received (for example, patients were randomized to the on-line pre-disclosure genetic education but instead received usual care).

There is no plan to perform interim outcome monitoring for this study. Participating patient will be at minimal risk given the nature of the study. The study will be closely monitored for feasibility (Section [7.1.4](#)), and if feasible, information/data gathered would be useful and informative in patient care.

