7.1.3 *Exploratory analysis* will be longitudinal changes in cognitive (e.g. genetic knowledge), affective (cancer specific distress, state anxiety, general anxiety and general depression, perceived utility, uncertainty). In these analyses, multiple linear or logistic regressions will be fit to investigate temporal changes in the randomization arm effect, using the Generalized Estimating Equations (GEE) to account for correlated data over time. Unstructured working correlation matrices for GEE will first be considered unless there are model convergence problems, in which case exchangeable working correlation matrices will be used instead. In the regressions, survey wave and the randomized arm will be included as dummy indicator (0/1 variables) covariates. As there are four survey time points, we include three dummy indicators for T1, T2 and T3. In analyzing the change of scores (T1-T0, T2-T0, T3-T0), two dummy indicators will be needed. We will also include interactions between the survey wave indicators and the arm indicator to see if the arm effect changes over time. We will also include potential baseline confounding variables that were not balanced between arms at a p-value < 0.1 (using T-Tests and Fisher's Exact Tests). These analyses will be repeated using the as-treated approach as well.

To evaluate potential moderators as described in Section [2](#), we will add relevant interaction terms to the GEE-estimated multiple linear and logistic regressions described above. Of most interest are interactions between the potential moderators (e.g. test result, sociodemographic factors, health literacy, baseline knowledge or distress) and the arm indicator.

Other exploratory endpoints include satisfaction and regret/disappointment related to tumor genetic test results, and how to better deliver tumor genetic test results and germline information in the future. Summary statistics will be provided and comparison may be explored between arms using T-Tests or Fisher's Exact Tests at two-sided significance level of 0.05.

Rev. 7/17

7.1.4 *Feasibility*

Monitoring enrollment on the primary study:

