Changes in knowledge and distress (state anxiety, general anxiety, general depression and cancer specific distress) from baseline to post-pre-test genetic counseling (T0SS to T1SS) and baseline to post-test for those who proceed with confirmatory genetic testing (T0SS to T2SS) will be described using descriptive statistics (e.g. means, standard deviations, proportions, 95% confidence intervals). Multiple linear regressions will be fit to further investigate temporal changes. Again, regression parameters will be estimated using GEE to account for correlated data over time. Unstructured working correlation matrices for GEE will be considered first unless there are model convergence problems, in which case exchangeable working correlation matrices will be used instead. In the regressions, survey wave as dummy indicator (0/1 variables) will be included as covariates. As there are three survey time points, we include two dummy indicators for T1 and T2 (leaving T0 as the baseline reference time period). We will also include potential baseline confounding variables in the models (e.g. age, sociodemographic variables).

Other exploratory endpoints include communication to others, satisfaction and regret/disappointment related to genetic counseling service or germline genetic test results. Summary statistics will be provided.

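### Step 1 covariates are chosen by testing baseline balance at p < 0.1, a screen that ignores prognostic value and rarely admits the factors the trial stratified on

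*Combined protocol and SAP*

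**What the plan says.** - **Primary analysis (7.1.2).** An unadjusted two-sample t-test with unequal variances on each change score, at the two-sided 0.005 level set in 7.1.1. No covariates.
- **Secondary regressions (7.1.2).** First, "demographic characteristics between the two arms will be evaluated using T-tests and Fisher's Exact Tests". The variables of main interest are given as "in particular age, race/ethnicity and health literacy". If any differ between arms at p < 0.1, a linear regression is fitted in which "all potential confounders that have a p-value < 0.1 will be included as covariates". If none differ, no adjusted model is called for. The analyses are then repeated as-treated.
- **Longitudinal GEE models (7.1.3).** The same rule: "We will also include potential baseline confounding variables that were not balanced between arms at a p-value < 0.1". An as-treated repeat follows here too.
- **Moderator models (7.1.3).** These add to the GEE models "interactions between the potential moderators (e.g. test result, sociodemographic factors, health literacy, baseline knowledge or distress) and the arm indicator".
- **Design.** Section 7.1.1 states that "the randomization will be stratified by gender, race, age (> 65 vs. ≤ 65), and education level". Section 4.1.3.2 defines the race factor as "Race: White vs. Others" and education in three levels. Section 5.1.1 specifies 1:1 permuted blocks.

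No Step 1 text enters the stratification factors as covariates regardless of balance. Nor does the plan say on which set the balance tests are run: all randomised, T0+T1 completers, T0+T2 completers, or the as-treated groups.

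**The concern.** A baseline test between randomised arms asks whether an imbalance is larger than chance would produce, when chance is already known to be the cause. What matters for adjustment is whether the variable predicts the outcome, and the p-value carries no information on that. A strongly prognostic but balanced variable is left out, and an irrelevant one that happens to be imbalanced is put in.

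The rule also works against the design. Stratification makes the arms alike on gender, race group, age group and education, so these are the variables least likely to pass. Yet 7.1.2 names age and race/ethnicity as covariates of particular interest.

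At stake are the plan's only covariate-adjusted look at the ten primary comparisons, and the longitudinal models on which the moderator analyses (secondary objective, 2.2.1) are built.

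**Working it through.** **1. The plan's own figure.** Knowledge, T0 to T2, 150 per arm (7.1.1): changes 5.86 and 4.40, SDs 4.30 and 3.05, two-sided alpha 0.005.
- Difference = 5.86 − 4.40 = 1.46.
- SD = √((4.30² + 3.05²)/2) = 3.728.
- Standard error = 3.728 × √(2/150) = 0.4305.
- Power = Φ(1.46/0.4305 − 2.807) = Φ(0.585) = 72.1%. The plan states 72%; a Welch noncentral-t calculation gives 71.2%.

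**2. How often each variable passes the screen.** The check used 2,000 simulated trials per scenario.
- From the documents: 670 patients; 2 × 2 × 2 × 3 = 24 strata; 1:1 permuted blocks; 591/670 = 88% White (7.3.1); 60% (T0+T1) and 45% (T0+T2) survey completion (7.1.1).
- Assumed, because not given: block size 4 (8 also tried with all 670), 50% female, age mean 62 and SD 11, education split 35/40/25.
- Tests: Fisher for two-level factors, chi-square in place of Fisher for education, t-test for mean age and health literacy.

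| Scenario | Each categorical stratification factor | Any of the four | Any of the four, age tested as a mean | Health literacy (unstratified) |
|---|---|---|---|---|
| All 670, blocks of 4 or 8 | 0.0% | 0.0% | 0.6 to 1.0% | 10.6 to 11.8% |
| 60% evaluable, missing at random | 0.2 to 1.3% | 3.3% | 6.5% | 10.4% |
| 45% evaluable, missing at random | 1.8 to 3.0% | 8.8% | 12.0% | 8.9% |
| 60% evaluable, arm-related non-response | 0.5 to 12.4% | 22.5% | 24.2% | 8.7% |
| All 670, no stratification | 7.3 to 9.7% | 28.5% | 30.2% | 9.6% |

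In the fourth row, completion in one arm shifts by an assumed 10 points per education level and by 10 points between age groups. Age group then passes in 9.7%, mean age in 12.0% and education in 12.4%. Simulation error on a rate near 10% is about √(0.1 × 0.9/2000) = 0.7 points.

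**3. What leaving the factors out costs.** Let R² be the share of outcome variance explained by the four factors. The documents do not give it; 0.02 to 0.20 is assumed. Treat the factors as fully balanced by stratification. For knowledge T0 to T2 at 150 per arm:
- Adjusted power = Φ(3.392/√(1 − R²) − 2.807).
- Unadjusted power = Φ((3.392 − 2.807)/√(1 − R²)).
- True type I error of the unadjusted test = 2 × (1 − Φ(2.807/√(1 − R²))).

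| R² | Adjusted power | Unadjusted power | True type I error of unadjusted test (nominal 0.005) |
|---|---|---|---|
| 0.02 | 73.2% | 72.3% | 0.0046 |
| 0.05 | 75.0% | 72.6% | 0.0040 |
| 0.10 | 77.9% | 73.1% | 0.0031 |
| 0.20 | 83.8% | 74.3% | 0.0017 |

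Ignoring the strata makes the test conservative. The precision that stratification provides is not carried into the analysis.

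**The case against.** **Imbalance is not always chance.** This stands in part. The as-treated groups are not randomised, and 40 to 55% of patients lack the paired surveys, so non-response could differ by arm. The simulated rate for any of the four then rises to 23 to 24%, which is not negligible. But even under that assumed mechanism, age and education, the two variables driving it, each passed in only about 10 to 12% of trials. The screen mostly misses the problem it might be meant to catch.

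**Stratification does not cover everything named.** This stands. Ethnicity is not stratified, and age is stratified only at 65, so mean age can still differ. The table therefore shows mean age separately.

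**The rule is prespecified and never looks at outcomes.** This stands. It gives no room to pick covariates by result.

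**Stronger readings a reader might infer, which the documents do not support:**
- That every GEE model is affected. The Step 2 models (7.2.2) name age and sociodemographic variables as covariates with no balance test. The Step 1 moderator models bring in named factors through interactions, although the underlying models still follow the screen.
- That a spurious covariate enters about half the time. The chance that at least one of k independent unstratified variables passes is 1 − 0.9^k, and the plan does not give k. Health literacy alone gives 10%; adding ethnicity gives 1 − 0.9² = 19%.
- That the ten endpoints would carry many different covariate sets. All instruments form one survey per timepoint, so there would be essentially two sets, or one if all randomised patients are screened.
- That the primary conclusions are at risk. The primary t-tests contain no covariates.

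**Conclusion.** The concern holds for the Step 1 secondary regressions and longitudinal GEE models. The screen selects on a quantity unrelated to prognosis, and the stratification factors seldom pass it when data are complete or missing at random.

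The consequence is lost precision and unstable adjustment, not invalid inference. At R² = 0.10, for example, adjusted power for knowledge T0 to T2 is 77.9% against 73.1% unadjusted. That is a gain for the secondary analysis; it does not change the power of the primary test.

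The pass rates depend on the assumed block size and prevalences, though blocks of 4 and 8 gave the same 0.0% for categorical factors in all 670. The power range rests wholly on the assumed R². The type I figures assume complete balance on the factors; with surveys missing at random the true values lie between those shown and 0.005. This is a change that should be made, but nothing in the primary analysis depends on it.

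**What to change.** In 7.1.2 and 7.1.3, drop the p < 0.1 screen as the covariate rule and fix one list for the Step 1 secondary regressions and GEE models:
- gender, race, age and education, whatever their observed balance;
- health literacy;
- the baseline score of the outcome, in the change-score models.

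Moderator models should also contain the main effect of each moderator tested. Fit the adjusted models in every case, not only when an imbalance is seen. Report baseline characteristics by arm descriptively, including for the T0+T1 and T0+T2 evaluable sets and the as-treated groups, so that imbalance from non-response or crossover stays visible. The Step 2 models need no change on this account.

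The cost is a wording change and a few degrees of freedom: 1 + 1 + 1 + 2 + 1 + 1 = 7 with the baseline score, if age and health literacy each enter as one term, against about 300 patients in the smaller evaluable set. All variables are already collected, at registration or in the T0 survey. Patients without T0 are off study under 4.3, so the list should remove few if any evaluable patients.

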- Staff to track survey completion and contact participants when a survey is late.
- Staff to identify when a participant has received their tumor genetic testing results and upload the test report into the Rave system.

Rev. 7/17

4.1.5 Registration of a patient to the COMET Ancillary Study Protocol does not relieve the registering investigator from adhering to correlative study requirements specific for the MATCH or other molecular profiling protocol and not specified by this ancillary protocol.

4.1.6 Patients assigned to the web-based education who do not view the website but complete baseline survey will still complete follow-up surveys.

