5.2 Interventions

Rev. 2/17
Rev. 7/17

5.2.1 Primary Intervention Study (RCT) (Step 1):

As shown in the study schema, participants will be randomly assigned to web-based genetic education or a control group receiving usual care.

- Genetic education website (Arm A – intervention group):

Upon completion of the baseline survey, Arm A participants will receive an access code to enter and complete the online education module. Adapted for COMET participants from the COMET pilot study materials, the module is designed to provide information on what can be learned through tumor testing, including the differences between genetic tumor changes and potential germline findings, and next steps including confirmation testing should a germline mutation be suspected. The module, which will be content and usability tested with patients of varied background and cancer diagnosis, features simple text, graphic, and video components.

Arm A participants will be offered access to the web-based genetic education module at the study site following completion of the baseline survey, and will be able to revisit the site using any computer with web access, including a smart phone.

- Usual care (Arm B - control group):

Participants in the usual care arm will not initially have access to the web-based genetic education. Rather their education will be consistent with usual care including conversations with the treating physicians, interaction with and information from clinical and/or MATCH research staff and any additional information they seek out through usual resources. This is intended as a “real world” comparison group. All usual care arm participants will be provided access to on-line genetic web education three months after receiving their tumor genetic testing results. These patients will be e-mailed a link to the website and a code to access the materials, which are viewable on any web-enabled device.

- Both Arms (A & B):

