5.8 Duration of Follow-up

For this protocol, all patients, including those who do not complete all steps, will be followed until the time of their last planned survey. Individual activity on the online genetic education web site will be followed through completion of all protocol therapy (if enrolled in MATCH).

In addition, all patients will be followed for survival per the standard ECOG-ACRIN follow-up schedule: at 3 months and 6 months after study entry.

Rev Add7 **6. Study Parameters**

Rev. 2/17

NOTE: All patients enrolled into Step 1 (including Arms A, B, and C) will be followed for survival per the standard ECOG-ACRIN follow-up schedule: at 3 months and 6 months after study entry.

Below is information specifically for patients enrolled into Arms A and B for the primary study.

Rev. 7/17
Rev Add7

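### The as-treated repeats compare self-selected viewers with everyone else; at T1 and T2 a complier-average effect would answer the same question and keep the randomised comparison

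*Combined protocol and SAP*

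**What the plan says.** All references are to the combined protocol and SAP.

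- **Primary analysis (7.1.2).** "An intention-to-treat approach will be used in which the effect between randomized arms is evaluated, regardless of any treatment crossover". This is a two-sample t-test with unequal variances on change scores.
- **Secondary repeat (7.1.2).** "These analyses will be repeated using the as-treated approach in which we compare differences between the interventions the patient actually received". The example given is that "patients were randomized to the on-line pre-disclosure genetic education but instead received usual care".
- **Longitudinal models (7.1.3).** After the GEE models, which run to T3: "These analyses will be repeated using the as-treated approach as well".
- **Covariates (7.1.2, and similarly 7.1.3).** Adjustment is for potential confounders "found to have means/proportions that are different between the arms at a p-value of less than 0.1". Age, race/ethnicity and health literacy are singled out.
- **Access (5.2.1).** "Participants in the usual care arm will not initially have access to the web-based genetic education". They receive it three months after their tumour results.
- **Non-viewers (4.1.6).** "Patients assigned to the web-based education who do not view the website but complete baseline survey will still complete follow-up surveys".
- **Logs (5.8).** "Individual activity on the online genetic education web site will be followed". The sentence ends with a qualifier about MATCH enrolment.
- **Reporting (7.1.4).** The plan will report crossover and the share of Arm A that completes the module.

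The plan does not define what counts as having received the education (any opening, or the whole module). It has no complier-average or instrumental-variable analysis.

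**The concern.** Arm A patients who do not open the module are regrouped with usual care. Opening it is voluntary and may go with health literacy, motivation or distress. The plan's own theory (Sections 1.2 and 2.2.1) expects health literacy, baseline knowledge and distress to shape the outcome changes. The regrouped contrast therefore mixes the effect of the module with the kind of patient who opens it.

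The covariate rule does not repair this. It screens for differences between randomised arms, not between viewers and non-viewers, and motivation is not among the measures in Section 6.1.

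The as-treated repeat is the plan's only estimate of what receiving the education does, and it carries no caveat. It could show a difference when the module has no effect.

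**Working it through.** **1. Inputs.** From the documents:
- 1:1 allocation (5.1.1) and a two-sided 0.005 level for the primary analyses (7.1.1)
- knowledge T0–T2 change of 5.86 against 4.40, with SDs 4.30 and 3.05 (7.1.1 table)
- 150 evaluable per arm at T2, with 72% power (7.1.1)

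Assumed, because the documents give no value:
- viewing rate p in Arm A, 0.5 to 0.9
- viewer minus non-viewer gap g in change score that exists without any module effect, 0.3 or 0.5 SD

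**2. The plan's own figure.** Difference = 5.86 − 4.40 = 1.46. Pooled SD = √((4.30² + 3.05²)/2) = 3.73. SE at 150 per arm = √((4.30² + 3.05²)/150) = 0.43. Power at two-sided 0.005 is 0.721 (normal approximation) or 0.712 (Welch), against the stated 72%. The inputs are read correctly.

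**3. Who is compared.** With n per arm and no Arm B access, the received group is the np viewers in Arm A. The not-received group is n(1 − p) Arm A non-viewers plus n Arm B patients, of whom np would have viewed if offered.

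**4. Bias.** Let τ be the true effect in viewers. The received mean is g + τ. The not-received mean is g·p/(2 − p). So

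as-treated difference = τ + g·2(1 − p)/(2 − p).

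With τ = 0 and g = 0.3 SD, for example at p = 0.6: 0.3 × 0.8/1.4 = 0.17 SD. With τ = 0.3 SD the same setting gives 0.30 + 0.17 = 0.47 SD.

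**5. On the knowledge scale with no true effect** (SD 3.73). Rejection rates are from simulation with 200 per arm and 3,000 runs per setting. The plan states no threshold for the as-treated repeats, so the primary 0.005 is used.

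| p | Bias in SD, g = 0.3 | Points, g = 0.3 | Rejected, g = 0.3 | Points, g = 0.5 | Rejected, g = 0.5 |
|---|---|---|---|---|---|
| 0.9 | 0.05 | 0.20 | 1.2% | 0.34 | 2.2% |
| 0.8 | 0.10 | 0.37 | 3.1% | 0.62 | 11.6% |
| 0.7 | 0.14 | 0.52 | 6.6% | 0.86 | 25.7% |
| 0.6 | 0.17 | 0.64 | 10.6% | 1.07 | 40.5% |
| 0.5 | 0.20 | 0.75 | 12.8% | 1.24 | 51.0% |

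With g = 0 there is no bias and rejection is about 0.5%. In the same runs the intention-to-treat test rejected 0.3% to 0.8% of the time, and the complier estimate centred within about 0.03 points of zero. At g = 0.5 and p = 0.7 to 0.6, the spurious difference is 0.86/1.46 = 59% to 1.07/1.46 = 73% of the planned difference.

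**6. The alternative.** Without covariates, complier effect = intention-to-treat difference / p, with SE about SE/p. For knowledge T0–T2 at 150 per arm, if the intention-to-treat difference is 1.46:

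| p | Complier effect | SE |
|---|---|---|
| 0.9 | 1.62 | 0.48 |
| 0.8 | 1.82 | 0.54 |
| 0.7 | 2.09 | 0.61 |
| 0.6 | 2.43 | 0.72 |
| 0.5 | 2.92 | 0.86 |

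Estimate and SE scale together, so the test of no effect is essentially the intention-to-treat test.

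**7. Why exposure should be any opening.** Suppose 60% complete the module, a further 20% view part of it, and both groups gain 0.3 SD. The intention-to-treat difference is 0.8 × 0.3 = 0.24 SD. Dividing by completion gives 0.24/0.6 = 0.40 SD, a third too high. Dividing by any opening gives 0.24/0.8 = 0.30 SD. If partial viewers gain half as much, the completion version gives (0.18 + 0.03)/0.6 = 0.35 SD.

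**The case against.** **Only secondary and exploratory analyses are affected.** This stands. A reader might infer that the trial's main conclusion is at risk. It is not, because the primary comparison is by randomised arm.

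**The bias may be small.** This partly stands. Arm A is offered the module at the study site straight after baseline, so uptake could be high; at 90% and g = 0.3 the bias is about 0.05 SD. Repeating the analyses could also mean repeating the imbalance check between received groups, which would adjust for some measured differences, health literacy among them. It would not remove unmeasured ones.

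**Direction.** A reader might infer that as-treated will favour the module. The documents do not support that. Four of the five primary outcomes are distress or mood scores, and viewers could be the more or the less distressed patients.

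**The complier estimate has its own assumptions.** This stands. An unopened offer must have no effect. A reader might also take the estimate to be fully protected by randomisation. It is not: analysis is of survey completers, about 60% at T0 and T1 and 45% at T0 and T2 (7.1.1), and the estimate inherits that selection, as the intention-to-treat analysis does.

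**It does not fit everywhere.** This stands. The T3 survey and Arm B access both fall three months after results, so one-sided access is doubtful there. Two-stage least squares is also not a direct substitute for the linear and logistic GEE models in 7.1.3.

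**The logs may not cover everyone.** This is open. The MATCH qualifier in 5.8 may limit only how long activity is tracked, and 7.1.4 plans to report Arm A completion without restriction. But non-MATCH patients are eligible, so coverage should be confirmed.

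**Conclusion.** The point holds for the secondary and exploratory as-treated repeats. At T1 and an on-time T2 they compare self-selected viewers with a mixture of non-viewers and controls, and the covariate rule is not aimed at that difference. With no true effect and an assumed 0.3 SD viewer gap, the spurious difference is about 0.05 to 0.20 SD for viewing between 90% and 50%. These figures are unadjusted, rest on assumed gaps and viewing rates, and vanish if viewers and non-viewers would change alike.

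The stronger reading, that every as-treated analysis must be replaced, goes too far. The design supports a complier estimate for the T1 and T2 change scores, because access is one-sided by plan, non-viewers stay in follow-up and site activity is tracked. It does not clearly support one at T3. This is a cheap improvement, not a flaw in the primary analysis.

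**What to change.** - For the T0–T1 and T0–T2 change scores, make the secondary analysis of receipt a complier-average effect. Use two-stage least squares with randomised arm as instrument and the same covariates as the corresponding regression by randomised arm.
- Define exposure as any opening of the module before the relevant survey. Use completion only as a sensitivity analysis, because partial viewing breaks the exclusion assumption.
- Compute uptake in the same evaluable set as the outcome, and report it by arm.
- If as-treated results are kept, including the GEE and T3 models in 7.1.3, label them descriptive and non-randomised.
- Check completion dates of late T2 surveys against the date of Arm B access, since Section 5.4 keeps surveys open until they are completed or the patient is off study.
- Confirm that website logs cover non-MATCH patients, and clarify the qualifier in 5.8.

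The cost is SAP wording, a standard routine for the two change scores, and the log and date checks. No new data are needed where logs are held. The downsides are a wider interval, the exclusion assumption, and the same survey-completer selection that the intention-to-treat analysis carries.
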